## **6.4. Analysis of safety**

### **6.4.1. Analysis of safety planned in the protocol**

The ES will be used for the analysis of safety.

The following calculations will be performed for each group and for the pooled liquid vaccine group:

The percentage of doses and of subjects reporting at least one symptom (solicited or unsolicited) during the 8 days (Day 0-Day 7) solicited follow-up period post vaccination will be computed, along with exact 95% CI. The same calculations will be done for symptoms (solicited or unsolicited) rated as grade 3 in intensity and for symptoms (solicited or unsolicited) assessed as causally related to vaccination.

The percentage of doses and of subjects reporting each individual solicited general symptom will be computed, over the 8 days (Day 0-Day 7) solicited follow-up period post vaccination, along with exact 95% CI. The same calculations will be done for each individual general solicited symptom rated as grade 3 in intensity, for each individual solicited general symptom assessed as causally related to vaccination and those that resulted in a medically attended visit.

The verbatim reports of unsolicited AEs will be reviewed by a physician and the signs and symptoms will be coded according to MedDRA. Every verbatim term will be matched with the appropriate Preferred Term. The percentage of subjects with unsolicited AEs occurring within 31 days (Day 0-Day 30) follow-up period after any dose with its exact 95% CI will be tabulated by group, and by preferred term. Similar tabulation will be done for unsolicited AEs rated as grade 3, for unsolicited AEs with causal relationship to vaccination and those that resulted in a medically attended visit.

The percentage of subjects reporting GE episodes from Dose 1 of HRV vaccine up to Visit 3 will be tabulated by group.

The percentage of subjects with presence of RV in GE stool samples collected from Dose 1 of HRV vaccine up to Visit 3 will be tabulated by group.

The percentage of GE episodes with no available stool results from Dose 1 of HRV vaccine up to Visit 3 will be tabulated.

The percentage of subjects who started taking at least one concomitant medication from HRV vaccination to Day 7 after vaccinations will be tabulated with exact 95% CI. The percentages of subjects who started taking at least one concomitant medication during the study period will be tabulated with exact 95% CI.

SAEs reported during the study period will be described in detail.

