#### 6.4.2. Additional considerations

As indicated in section 10.5 of the protocol and in line with the project history, analysis of safety will be primarily performed per dose administered and subjects who missed reporting symptoms (solicited/unsolicited or concomitant medications) will be treated as subjects without symptoms (solicited/unsolicited or concomitant medications, respectively). A sensitivity analysis will be performed on documented doses i.e. accounting only for doses where solicited symptoms are indicated as being absent/present in case more than 5% of the doses are not documented.

Summary of temperature will be provided by 0.5° increment (i.e.  $\geq 38.0^{\circ}\text{C}$ ,  $>38.5$ ;  $> 39$ ,  $> 39.5$ ,  $> 40$ ).

Gastroenteritis is assumed to take place when either:

- a stool collection is reported
- three or more than 3 loose stools are reported as solicited diarrhoea symptom.
- an unsolicited symptom, which has an onset date more than 7 days after vaccination (i.e. with onset day  $> 8$ ), is associated with the high lever MedDRA terms hereunder but excluding Diarrhoea as primary preferred term (10012735): ‘Gastric and gastroenteric infections’ (10017887), ‘Gastrointestinal infections, site unspecified’ (10017968), ‘Intestinal infections (10022678)’, ‘Faecal, abnormalities NEC’ (10016097), ‘Diarrhoea (excl infective)’ (10012736).

Summary of solicited symptoms will also be provided by country, gender and frequent race(s) while summary of unsolicited symptoms within 31 days post-vaccination will be provided by country – see section 6.3.2 for the definition of frequent race.

Summary of solicited symptoms will also be provided for each individual general solicited symptom causally related to vaccination and rated as grade 3 in intensity. Likewise the percentage of subjects and of doses with grade 3 causally related unsolicited AEs occurring within 31 days (Day 0-Day 30) follow-up period after any dose with its exact 95% CI will be tabulated by group, and by preferred term. These summaries will not be provided by country, gender or frequent race(s).

[figure not shown]
Note that the study will be converted in cDISC. Accordingly Day 0-Day 7 and Day 0-Day 30 will be replaced by Day 1-Day 8 and Day 1-Day 31 for the statistical analysis.

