#### 11.1.5. Safety

- For analysis of solicited, unsolicited adverse events (such as serious adverse events or adverse events by primary MedDRA term) and for the analysis of concomitant medications, all vaccinated subjects will be considered. Subjects who did not report the event or the concomitant medication will be considered as subjects without the event or the concomitant medication respectively.
- In case there will be more than 5% of subjects without documented dose for solicited symptoms (i.e., symptom screen not completed), sensitivity analysis will include only vaccinated subjects for doses with documented safety data (i.e., symptom screen completed).

- The following rules will be used for the analysis of solicited symptoms:
  - Subject who didn't document the presence or absence of a solicited symptom after one dose will be considered not having that symptom after that dose in the analysis done on "administrated dose"
  - Subjects who documented the absence of a solicited symptom after one dose will be considered not having that symptom after that dose.
  - Subjects who documented the presence of a solicited symptom and fully or partially recorded daily measurement over the solicited period will be included in the summaries at that dose and classified according to their maximum observed daily recording over the solicited period.
  - Subjects who documented the presence of a solicited symptom after one dose without having recorded any daily measurement will be considered as having that symptom after that dose).

- For the analysis, temperatures will be coded as follows for oral, axillary or tympanic route:

Grade	Temperature
0	< 38.0°C
1	≥ 38.0°C - < 38.5°C
2	> 38.5°C - < 39.5°C
3	> 39.5°C

- Note that for all tables described in this section, the way the percentage of subjects will be derived will depend on the event analysed (see table below for details). As a result, the N value will differ from one table to another.

Event	N used for deriving % per subject for Vaccination phase	N used for deriving % per dose for Vaccination phase
Concomitant vaccination	All subjects with study vaccine administered	All study visits with study vaccine administered

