Solicited general symptom	Primary analysis: all subjects with study vaccine administered Sensitivity analysis as applicable (see section 6.4.2): all subjects with at least one solicited general symptom documented as either present or absent (i.e., symptom screen completed)	Primary analysis: all study visits with study vaccine administered Sensitivity analysis: all study visits with study vaccine administered and with at least one solicited general symptom documented as either present or absent (i.e., symptom screen completed)
Unsolicited symptom	All subjects with study vaccine administered	All study visits with study vaccine administered
Concomitant medication	All subjects with study vaccine administered	All study visits with study vaccine administered

For summaries by MedDRA primary preferred term combining solicited and unsolicited adverse events, solicited adverse events will be coded as per the following MedDRA codes

Solicited symptom	Lower level term code	Corresponding Lower level term decode
Fever	10016558	Fever
Irritability/Fussiness	10022998	Irritability
Diarrhoea	10012727	Diarrhoea
Vomiting	10047700	Vomiting
Loss of appetite	10003028	Appetite lost
Cough/runny nose	10011224	Cough

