**Template 17 Compliance in returning symptom sheets - Exposed Set**

Dose	GROUP	Number of doses	Doses NOT according to protocol	Number of general SS	Compliance % general SS
1	LIQ_A	298	10	298	100
	LIQ_B	302	7	302	100
	LIQ_C	300	6	300	100
	LIQPOOL	900	23	900	100
	LYO	300	6	299	99.7
2	LIQ_A	297	12	296	99.7
	LIQ_B	301	6	301	100
	LIQ_C	300	13	299	99.7
	LIQPOOL	898	31	896	99.8
	LYO	299	9	297	99.3
Total	LIQ_A	595	22	594	99.8
	LIQ_B	603	13	603	100
	LIQ_C	600	19	599	99.8
	LIQPOOL	1798	54	1796	99.9
	LYO	599	15	596	99.5

LIQ\_A = HRV vaccine liquid formulation Lot A

LIQ\_B = HRV vaccine liquid formulation Lot B

LIQ\_C = HRV vaccine liquid formulation Lot C

LIQPOOL = Pooled HRV vaccine liquid formulation

LYO = HRV vaccine lyophilised formulation

SS = Symptom sheets used for the collection of solicited AEs

Compliance % = (number of doses with symptom sheet return / number of administered doses) X 100

Doses not according to protocol = number of doses with regurgitation or vomiting

**Template 18 Percentage of doses and of subjects reporting symptoms (solicited or unsolicited) reported during the 8-day (Day 0 to Day 7) follow-up period - Exposed Set**

	Group	Any symptom				
		N	n	%	95% CI	
					LL	UL
Dose 1	LIQ_A	298	251	84.2	79.6	88.2
	LIQ_B	302	267	88.4	84.3	91.8
	LIQ_C	300	247	82.3	77.5	86.5
	LIQPOOL	900	765	85.0	82.5	87.3
	LYO	300	249	83.0	78.3	87.1
Dose 2	LIQ_A	297	247	83.2	78.4	87.2
	LIQ_B	301	260	86.4	82.0	90.0
	LIQ_C	300	236	78.7	73.6	83.2
	LIQPOOL	898	743	82.7	80.1	85.2
	LYO	299	247	82.6	77.8	86.7
Overall/dose	LIQ_A	595	498	83.7	80.5	86.6
	LIQ_B	603	527	87.4	84.5	89.9
	LIQ_C	600	483	80.5	77.1	83.6
	LIQPOOL	1798	1508	83.9	82.1	85.5
	LYO	599	496	82.8	79.5	85.7
Overall/subject	LIQ_A	298	283	95.0	91.8	97.2
	LIQ_B	302	287	95.0	91.9	97.2
	LIQ_C	300	275	91.7	87.9	94.5
	LIQPOOL	900	845	93.9	92.1	95.4
	LYO	300	279	93.0	89.5	95.6

LIQ\_A = HRV vaccine liquid formulation Lot A      LIQ\_B = HRV vaccine liquid formulation Lot B  
 LIQ\_C = HRV vaccine liquid formulation Lot C      LIQPOOL = Pooled HRV vaccine liquid formulation  
 LYO = HRV vaccine lyophilised formulation

For each dose:

N = number of subjects having received the considered dose

n/% = number/percentage of subjects reporting at least one symptom for the considered dose

For overall/dose:

N = number of administered doses

n/% = number/percentage of doses followed by at least one symptom

For overall/subject:

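### Do the two 5% triggers for the documented-dose sensitivity analysis of solicited symptoms (doses in SAP 6.4.2, subjects in SAP 11.1.5) put the reactogenicity results at risk?

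*SAP*

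**What the plan says.** Protocol 10.5 sets the primary rule, and SAP 6.4.2 repeats it: "subjects who missed reporting symptoms (solicited/unsolicited or concomitant medications) will be treated as subjects without symptoms". SAP 6.4.2 then adds a sensitivity analysis restricted to documented doses, to be done "in case more than 5% of the doses are not documented".

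SAP 11.1.5, part of the annex of standard derivation rules, introduces the same analysis with a different unit: "In case there will be more than 5% of subjects without documented dose for solicited symptoms". The denominator table later in 11.1.5 labels the per-subject row "Sensitivity analysis as applicable (see section 6.4.2)" and defines its N as "all subjects with at least one solicited general symptom documented as either present or absent (i.e., symptom screen completed)".

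SAP 6.4.1 plans both kinds of rate: "The percentage of doses and of subjects reporting each individual solicited general symptom will be computed". Template 17, "Compliance in returning symptom sheets", gives sheets returned by dose number and group, with no threshold attached. Template 28 is a drafted layout for the documented-dose table.

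**The concern.** Two sentences give one analysis two conditions. They can disagree, because an infant has two doses and may miss the card for only one of them. The phrase in 11.1.5 is also open: a subject without a documented dose may be one with any dose undocumented, or one with none documented. The level is left open too, although the 5% rule for the Exposed Set immunogenicity analysis in SAP 6.3.1 is explicitly per group.

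At stake is the planned check on counting missing as absent. If card return differed between the lyophilised and liquid groups, the primary rule would lower the rate more in the group with poorer return and create an apparent difference in reactogenicity. A trigger read over the whole trial might stay silent in that situation.

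**Working it through.** The 5% is a chosen threshold, so there is no derived figure to reproduce. The check asks when the readings disagree and what would then be lost. Non-return is assumed unrelated to symptoms throughout.

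**Inputs.** 1600 infants, 400 per group (protocol 10.3); two doses each, so 3200 doses (assumes every infant receives both). Return and symptom counts come from the mock Templates 17 and 19 to 21, copied from ROTA-061.

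**When the units disagree.** Let *a* infants miss one card and *b* miss both.

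- Share of doses: (a + 2b)/3200
- Share of subjects with any dose undocumented: (a + b)/1600
- Share of subjects with no dose documented: b/1600

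| Pattern | Doses | Subjects, any | Subjects, none |
|---|---|---|---|
| a = 81, b = 0 | 2.53% | 5.06% | 0% |
| a = 160, b = 0 | 5.00% | 10.0% | 0% |
| a = 161, b = 0 | 5.03% | 10.06% | 0% |
| a = 0, b = 81 | 5.06% | 5.06% | 5.06% |

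Read overall, the rules split between 81 and 160 one-card infants under the *any* meaning, and from 161 upward under the *none* meaning. They agree when every affected infant misses both cards.

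**What is lost in the one-card cases.**

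- *Per dose.* Where the dose rule is silent, at most 5% of doses are undocumented overall, so a true 70% would read no lower than 0.70 × 0.95 = 66.5% overall. The documented-dose rate is the symptom count in Template 19 or 20 divided by the sheets returned in Template 17. For mock LIQ_A irritability at Dose 2 this is 201/296 = 67.9%, against 201/297 = 67.7% in the primary table; 67.9% is also the entry in Template 28.
- *Per subject.* The sensitivity N in 11.1.5 keeps any infant with one completed screen. An infant missing one card stays in N and the missing dose adds no symptom, so the sensitivity result equals the primary one.

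**At the documented return rate.** Mock non-return is 2/1798 = 0.11% of liquid doses and 3/599 = 0.50% of Lyo doses, together 5/2397 = 0.21%. In subjects this is at most 5/1200 = 0.42% overall and 3/300 = 1.0% in Lyo. Every reading is far below 5%. A 70% symptom is understated by 70 × 2/1798 = 0.08 points in pooled liquid and 70 × 3/599 = 0.35 points in Lyo.

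**Unequal return (hypothetical).** Assume 9% non-return in Lyo and 1% in liquid. Then 72 + 24 = 96 doses, and 96/3200 = 3.0% overall, so a dose rule read overall is silent, while 72/800 = 9.0% in Lyo would fire per group. A common 70% would read 0.70 × 0.91 = 63.7% against 0.70 × 0.99 = 69.3%. Template 17 would print 91% and 99% return by group, and 0.637/0.91 = 0.693/0.99 = 70.0%.

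**The case for a change.** The strongest reply is that Template 17 does not rescue the per-subject rate. Take mock LIQ_A irritability (213/298 = 71.5% at Dose 1, 201/297 = 67.7% at Dose 2, 254/298 = 85.2% per subject) in a group of 400 with 9% of cards missing at each dose. If 36 infants miss both cards, the per-subject figure reads 0.852 × 0.91 = 77.6% (unrounded inputs). If 36 miss Dose 1 only and 36 others miss Dose 2 only, it reads 0.852 − 0.09 × (0.852 − 0.677) − 0.09 × (0.852 − 0.715) = 82.4%. Template 17 shows 91% return in both cases.

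The arithmetic is right, but it carries little weight here. The 9% is an assumption with no support in the documents. In the one-card version the planned sensitivity table would still read 82.4%, because of its denominator, so the trigger is not the cause. SAP 5.3 also has subjects with undocumented solicited symptoms reported by group with no threshold. That count would be 36 in one case and 72 in the other, and with it (0.824 − 0.09 × 0.715 − 0.09 × 0.677)/0.82 = 85.2% is recovered. One limit applies: SAP 6.1.2 places that summary on the per-protocol set.

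Mixed patterns do leave something. With *b* = 79 and *a* = 2, doses are 160/3200 = 5.00% and subjects 81/1600 = 5.06%, so only the subject rule (*any* meaning) fires. The per-subject sensitivity result would then differ from the primary: ignoring the two one-card infants, 85.2% would read 0.852 × (1 − 79/1600) = 81.0%. Running the analysis when either condition is met covers this.

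Two drafting points also stand. The level is unstated, and the word documented is used in two ways: SAP 5.3 counts a dose as lacking documentation if any one symptom is blank, while the 11.1.5 table accepts a dose with at least one symptom recorded.

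**Conclusion.** The wording mismatch is genuine but has no consequence that requires a change. The two sentences have workable readings. Section 6.4.2 is the study-specific text and the annex table refers to it; alternatively, the analysis is run if either condition is met, since neither sentence forbids it below the threshold. Which tables are produced is set by the list of tables named in SAP section 10, which is not among these documents.

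The trigger affects only a descriptive table (SAP section 7) and no co-primary objective. Protocol 5.6.14 has unreturned cards chased. At the illustrative ROTA-061 return rate nothing fires under any reading and the understatement is at most 0.35 points for a 70% symptom in either arm. Printing the documented-dose table unconditionally would nearly duplicate the primary one. It would also not be clearly closer to the truth: if parents of symptom-free infants return fewer cards, documented-dose rates overstate incidence.

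This rests on return staying near the ROTA-061 level and on non-return being unrelated to symptoms. If return fell well below that level, or differed markedly between groups, Template 17 would show it by group and the analyst would have reason to run the sensitivity analysis whichever sentence is followed.

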## 7. ANALYSIS INTERPRETATION

Except for analyses addressing criteria specified in the co-primary objectives referred as confirmatory analyses, all the analyses will be descriptive/exploratory in nature. The use of these descriptive/exploratory analyses should be limited to support the confirmatory analyses or to generate hypothesis.

To control the overall type I error below 2.5%, the confirmatory objectives will be evaluated using a hierarchical procedure as shown in [Figure 1](#). A confirmatory objective will be reached if the associated criteria are met and the previous objectives have been met.

**Figure 1 Sequence for evaluating the study objectives in order to control the overall type I error below 2.5%**

## 8. CONDUCT OF ANALYSES

### 8.1. Sequence of analyses

Safety data that is as clean as possible will be analysed for IDMC review. Details of the review are described in an IDMC charter.

#### 8.1.1. Final analysis up to Visit 3:

An analysis will be conducted once all the study data up to Visit 3 are available and cleaned and Rota-IgA ELISA testing at 1-2 month post-dose 2 has been fully completed. The Clinical Study Report (CSR) with data up to Visit 3 will be used for the registration of PCV-free liquid vaccine in European Union (EU) and ‘rest of world’ countries.

The study report will include the following:

- All analysis of the serum anti-RV IgA antibody concentrations, 1-2 months after Dose 2 in the lyophilised and pooled liquid groups.
- All analyses of safety up to visit 3 and analysis of SAEs and AEs leading to drop out based on the database lock for the analysis.

### 8.2. Final analysis

If the previous analysis does not cover all study data, the study report will be amended when all data will be available. The study report amendment will include the additional safety information

The following table provides the plan for analyses excluding analyses dedicated to IDMC

Description	Analysis ID	Disclosure Purpose (IN=internal, CTRS=public posting, SR=study report and public posting)	Dry run review needed (Y/N)	Study Headline Summary (SHS) requiring expedited communication to upper management (Yes/No)	Reference for TFL
Final analysis up to Visit 3	E1_05	SR	Yes	Yes	TFL TOC first version – All TFLs as per database lock date
Final	E1_01	SR	No	Yes	TFL TOC first version - All TFLs

### 8.3. Statistical considerations for interim analyses

All confirmatory analyses will be conducted for the Final analysis up to Visit 3 and therefore no statistical adjustment for interim analyses is required.

## 9. CHANGES FROM PLANNED ANALYSES

Not applicable

## 10. LIST OF FINAL REPORT TABLES, LISTINGS AND FIGURES

The TFL TOC provides the list of tables/listings and figures needed for the study report. It also identifies the tables eligible for each analyses and their role (synopsis, in-text, post-text, SHS, CTRS,...). Note that all TFL aimed to be included as post-text are noted as post-text even if these are tabulation of individual data such as listing of SAE. The post-text material contains all source material for the study report and accordingly a post-text table may be redundant with an in-text table.

The mock tables referred under column named 'layout' can be found in [Annex 3](#) of this SAP.

The following group names will be used in the TFLs, to be in line with the T-domains:

Group order in tables	Group label in tables	Group definition for footnote
1	Liq_A	PCV-free HRV liquid vaccine - lot A
2	Liq_B	PCV-free HRV liquid vaccine - lot B
3	Liq_C	PCV-free HRV liquid vaccine - lot C
4	Liq pooled	PCV-free HRV liquid vaccine - Pooled Lot
5	Lyo	HRV Lyophilised vaccine

## 11. ANNEX 1 STANDARD DATA DERIVATION RULE AND STATISTICAL METHODS

### 11.1. Statistical Method References

The exact two-sided 95% CIs for a proportion within a group will be the Clopper-Pearson exact CI Clopper CJ, Pearson ES. The use of confidence or fiducial limits illustrated in the case of binomial. *Biometrika*. 1934;26:404-413.

The standardised asymptotic two-sided 95% CI for the group difference in proportions is based on the method described in the following paper: Robert G. Newcombe, interval estimation for the difference between independent proportions: comparison of eleven methods, *Statist Med*. 1998; 17, 873-890. The standardised asymptotic method used is the method six.

### 11.1.1. Date derivation

- SAS date derived from a character date: in case day is missing,  $\frac{PP}{D}$  is used. In case day & month are missing,  $\frac{PPD}{D}$  is used.
- Onset day for an event (ae, medication, vaccination, ...): the onset day is the number of days between the last study vaccination & the onset/start date of the event. This is 1 for an event starting on the same day as a vaccination. See SAS date derived in case the start date of the event is incomplete.

### 11.1.2. Dose number

- The study dose number is defined in reference to the number of study visits at which vaccination occurred. More specifically dose 1 refers to all vaccines administered at the first vaccination visit while dose 2 corresponds to all vaccinations administered at the second vaccination visit even if this is the first time a product is administered to the subject.
- Relative dose: the relative dose for an event (AE, medication, vaccination) is the most recent study dose given before an event. In case the event takes place on the day a study dose is given, the related dose will be that of the study dose, even if the event actually took place before vaccination. For instance, if an adverse event begins on the day of the study vaccination but prior to administration of the vaccine, it will be assigned to this dose. In case a study dose is not administered and an event occurs after the subsequent study dose (e.g. 2nd study dose), the relative dose of the event will be study dose associated to the subsequent study dose (e.g. dose 2).
- The number of doses for a product is the number of time the product was administered to a subject.
- The incidence per dose is the number of vaccination visits at which an event was reported among all vaccination visits.

